2.2 Secondary outcomes

2.2.1 Audiometry

AMTAS is a self-administrated audiometry procedure that have shown equivalence to manual audiometry (Elkeboom et al., 2013). Across all tested audiometrical frequencies (250 up to 8000 kHz), the mean difference between both procedures (self-administrated vs. manual) was about 0.1 dB HL (min = -3 dB HL at 250 Hz and max = 3.6 dB HL at 8000 Hz). Data analysis will focus on hearing threshold differences with both procedures in a nested model: ear-participant-investigator.

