### 3.4 Clini cal Evidence to Date

A clinical literature evaluation is maintained and has been updated in 2016 for the hearing aids. They are designed to amplify sound. The benefit of hearing aids has been shown in various studies (Kochkin, 2011). The evaluation includes an analysis of adverse events for Bernafon products as well as competitor devices. The basic benefit of hearing aids does not change with newly released devices.

A new literature search was completed in June of 2017 specifically for self-directed hearing test and fitting devices. In 2013 a study was completed by Eikelboom et al. to compare the results of standard audiometry to an Automated Method for Testing Auditory Sensitivity (AMTAS) system. The standard deviation between methods across frequencies was 6.4 dB. Using standard audiometry a 5 dB test retest difference is acceptable. The 6.4 dB difference using an AMTAS system is slightly higher than the expected but not significant. According to a study by Convery et al. (2015), self-directed hearing tests show good test-retest reliability. Also, a study was completed by Convery et al. (2017) with a combination system similar to the IMD in which subjects completed a self-directed hearing test and fitting. Fifty-five percent were able to complete the process with no errors at all. The results show the importance of good training material.

A risk assessment is performed for all new devices. The primary risk identified is the possibility of achieving incorrect screening results if there is too much background noise. For the study purposes the test will be completed in a clinic; therefore, this risk is not applicable. However, in everyday use the environment in which the system is used cannot be controlled. The risk is mitigated by providing training material for the consultant that describes the type of environment needed to run the hearing screening. Additionally, no adverse events for any currently marketed self-fit hearing instrument systems have been reported.

The current study will provide further data for self-directed hearing tests and fitting systems.

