### 11.4 Planned Analyses

The analysis and documentation will be done by the statistician using R (latest available and validated version) downloaded from the official Comprehensive R Archive Network (https://cran.r-project.org/). R-Studio IDE will be used to integrate the analysis to the report. R provides adequate packages for descriptive statistics (base, stats, and Rmisc), data visualisation (ggplot2), mixed effect models (Imer, ImerTest, and nIme), and principal component analysis (FactoMineR).

A linear mixed effect regression will be used on the IOI-HA questionnaire, chi-squared distribution on the preference test and a paired t-test on hearing thresholds. The principal component analysis will be made on different outcomes and explanatory variables combinations.

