1.1 Research question

The test should answer following research questions:

- 1. Narrative effect of fitting procedure: are different fitting procedures leading to differences in perceived benefit with hearing aids despite similar electro-acoustical performances? (Questionnaires)
- 2. Self-administrated audiometry: is AMTAS self-administrated audiometry equivalent to standard clinical procedure? (hearing loss thresholds)

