4.1 Analysis methods

Linear mixed effect regression will be used on the IOI-HA questionnaire, chi2 distribution on the preference test and paired t-test on audiometrical thresholds. Principal component analysis will be made on different outcomes and explanatory variables combinations.

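### The audiometry analysis leaves frequency unspecified and plans no per-frequency or agreement result, although it is meant to answer an equivalence question

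*SAP*

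**What the plan says.** Research question 2 (SAP 1.1; protocol 11.1 is worded almost identically) asks: "is AMTAS self-administrated audiometry equivalent to standard clinical procedure". The audiometry comparison is a secondary outcome, and two statements define its analysis.

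- **Model.** SAP 2.2.1 and protocol 11.4.3: "Data analysis will focus on hearing threshold differences with both procedures in a nested model: ear-participant-investigator". Protocol 5.2 says the same.
- **Test.** SAP 4.1 lists "chi2 distribution on the preference test and paired t-test on audiometrical thresholds"; protocol 11.4 lists "a paired t-test on hearing thresholds".

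The screening runs from 250 to 8000 Hz (protocol 8.1.1 and 8.2.1). Neither document says how the frequencies enter the analysis, or how the nested model and the t-test relate. Neither sets a margin, limits of agreement or a criterion on absolute differences.

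As its benchmark, SAP 2.2.1 reports that the mean difference in a cited validation study "was about 0.1 dB HL (min = -3 dB HL at 250 Hz and max = 3.6 dB HL at 8000 Hz". Protocol 3.4 adds, from the same study: "The standard deviation between methods across frequencies was 6.4 dB". It also names 5 dB as an acceptable test-retest difference in standard audiometry, but the analysis sections do not use that figure.

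**The concern.** A paired t-test judges the signed mean difference against zero. If all frequencies go into one mean, a screening that reads low in the bass and high in the treble can look unbiased. Even frequency by frequency, a non-significant result is not evidence of equivalence, and the mean says nothing about how far apart the two procedures are in an individual ear.

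This matters more here than in most crossover trials. Protocol 8.1.2 and 8.2 use the automated thresholds to calculate gain for both fittings. An error at a given frequency therefore enters both periods equally and drops out of the IMD-RMD comparisons of questionnaires, preference, speech and usage. The audiometry comparison is the main planned place where it could be seen, in a study described as the final validation before release (protocol 4.1).

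**Working it through.** **The plan's own figures.** No power, sample size or margin is given for audiometry. The only power calculation concerns the preference test (w = 0.65, 2 df, n = 24, stated power 0.82). It reproduces at 0.821 but has no bearing here. The cited 0.1 dB mean cannot be reproduced because values at the intermediate frequencies are not given; the midpoint of the two extremes is (-3 + 3.6)/2 = 0.3 dB.

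**Inputs.** Pooled mean 0.1 dB and extremes -3 and +3.6 dB (SAP 2.2.1); SD 6.4 dB (protocol 3.4), assumed to be the SD of individual differences; minimum n = 24 (SAP 3.1); two-sided alpha 0.05.

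**1. Pooled test.** Power comes from the noncentral t with noncentrality d√n/SD.
- d = 0.1, SD 6.4: noncentrality 0.1 × √24/6.4 = 0.077, rejection 0.051.
- Averaging 12 thresholds per person with an intraclass correlation of 0.2 (both assumed): SD = 6.4 × √[(1 + 11 × 0.2)/12] = 3.30, rejection 0.052.
- At n = 40 with SD 6.4, rejection is still 0.051.

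The 6.6 dB span between the extremes is thus flagged at about the false-positive rate.

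**2. Per-frequency test on the same data.** With two ears averaged, SD = 6.4 × √[(1 + r)/2]. The between-ear correlation r is not in the documents, so a range is shown.

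| r | SD (dB) | power, 3 dB | power, 3.6 dB |
|---|---|---|---|
| 0 | 4.53 | 0.87 | 0.96 |
| 0.8 | 6.07 | 0.64 | 0.79 |
| 1 (as one ear) | 6.40 | 0.59 | 0.75 |

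**3. Simulation.** 24 participants, two ears and 6, 8 or 11 frequencies; biases running from -3 to +3.6 dB with mean 0.1; total random SD 6.4, split between participant, ear and residual as 2/2/5.74 or 4/2/4.58 (assumed). The pooled test rejected in 5-6% of trials, a separate 250 Hz test in about 75-84%, and a test of trend over frequency in about 100%.

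**4. Individual scatter.** If differences are roughly normal around zero with SD 6.4:
- 95% limits of agreement: ±1.96 × 6.4 = ±12.5 dB.
- Beyond 5 dB: 2[1 - Φ(5/6.4)] = 43%. Beyond 10 dB: 2[1 - Φ(10/6.4)] = 12%.
- If thresholds are recorded in 5 dB steps (assumed), more than 5 dB apart means at least 10 dB, or 2[1 - Φ(7.5/6.4)] = 24%. More than 10 dB apart becomes 2[1 - Φ(12.5/6.4)] = 5%.

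**5. What the nested model can recover.** With the participant SD raised to 10 dB in the simulation, the pooled test still rejected in only 5% of trials while 37% of differences exceeded 10 dB. The participant variance component was nevertheless estimated correctly, at about 10 dB.

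**The case against.** A reader might infer more than the documents support, in four ways.

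**That the plan pools over frequency and judges only the signed mean.** It does not say so. The nesting statement describes grouping levels and need not list every fixed effect. SAP 2.2.1 itself quotes results at single frequencies, and per-frequency t-tests would fit the text. Pooling is the natural reading but not the only one. The defect is under-specification, and the 5% figure applies only if frequencies are pooled.

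**That large individual disagreement cannot show.** That is true of the t-test, not of the nested model, whose participant, ear and residual variances carry it (step 5). What stands is that the plan neither promises to report those variances nor sets a criterion for them.

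**That the benchmark shows a faulty screening.** It does not. Mean biases of -3 and +3.6 dB lie inside the 5 dB that protocol 3.4 calls acceptable. Power to find them different from zero answers a difference question, whereas an equivalence claim also needs the interval inside the margin. With SD 6.4 and n = 24 the 95% half-width is 2.07 × 6.4/√24 = 2.70 dB, so an observed 3.6 dB would have an upper limit of 6.3 dB.

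**That the wording of protocol 3.4 is part of this defect.** That section turns the SD into a difference: "The 6.4 dB difference using an AMTAS system is slightly higher than the expected but not significant". An SD describes scatter, so the sentence is loose. But it is background prose that sets no endpoint, margin or analysis, and this point does not rest on it.

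The study is also exploratory (protocol 6.1) and the outcome secondary. Protocol 11.4.7 allows reported post hoc work on secondary outcomes, so a per-frequency table could be added later. It would carry less weight than one planned before the data are seen.

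**Conclusion.** The concern holds as a gap in specification. The plan does not say how frequency is handled, and it names a test that cannot answer the equivalence question it sets. Under pooling, the SAP's own pattern of opposite errors would be flagged about 5% of the time. A per-frequency analysis of the same 24 participants would detect biases of that size with power of 0.64 to 0.96 for between-ear correlations of 0 to 0.8. The scatter figures (limits of about ±12.5 dB; 43% and 12% of differences beyond 5 and 10 dB, or 24% and 5% with 5 dB steps) depend on reading 6.4 dB as the SD of individual, roughly normal differences around zero. The between-ear correlation, number of frequencies, variance split and step size are assumptions. The documents do not support saying that the screening is inaccurate or that the planned model is bound to miss disagreement. The change should be made, but the trial does not stand or fall by it.

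**What to change.** In protocol 11.4 and 11.4.3 and SAP 2.2.1 and 4.1:

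1. Model the paired threshold difference with frequency as a fixed effect, keeping ear within participant within investigator as random, and report the variance components.
2. Report for each frequency the mean difference with 95% CI, the 95% limits of agreement, and the share of thresholds within ±5 and ±10 dB.
3. Judge equivalence by comparing these results with a margin stated in advance, in place of the paired t-test. The 5 dB test-retest figure in protocol 3.4 is a candidate; the sponsor should justify the choice and say which results it applies to.
4. State how thresholds above the automated test's 80 dB output limit (protocol 3.7 and 8.1.1) are analysed. The population extends to severe loss, and capped or missing values would distort the differences and the limits of agreement.
5. Make sure thresholds by ear, frequency and procedure are captured. The CRF list in protocol 12.1.1 names no audiometry field.

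The cost is one model term, one table and possibly a CRF field, with no extra visits or tests. The sponsor should expect the per-frequency result to look less favourable than a single mean.

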2.2.2 Data logging

The usage of hearing aids will be recorded as another indication of hearing aid use. The data will be averaged from each ear. Following data will be used:

- 1. Daily usage in hours per day,
- 2. Acoustical environment in percentage for following listening environments: quiet, speech in quiet, speech in noise, and noise.

2.3 Explanatory variables

2.3.1 Speech intelligibility Freiburger Test

The freiburger sprachtest is a standardized speech test in German speaking areas. Percentages of correctly repeated words are recorded as test outcomes by the investigator for the unaided and aided conditions for each test session.

Differences between unaided and aided (IMD vs. RMD) at 50% speech intelligibility will be used as an explanatory variable for the model.

2.3.2 Gothenburg profile

The perceived handicap associated with hearing impairment might also play a role in perceived benefit from hearing aid. The Gothenburg Profile (GP) is a 20 items questionnaire with a 5 points scale (how often...? never, rarely, sometimes, often, and always). First block of 10 questions addresses speech intelligibility and localization while second block is focused on experienced handicap and the relation to others.

Our hypothesis is that participants that are not often affected in their daily life by their hearing impairment, might report smaller benefit from amplification with a hearing aid. Understanding and quantifying their struggles with principal component analysis could be used to improve the modelling of the results.

3. Sample size and power analysis

Literature search about this tested topic does not provide enough strong references to build a confirmatory analysis. It seems that results might be strongly influenced by the inclusion criteria (first time vs experienced hearing aid users) or test design (cross-over, multi-site, or between group design). There is no article to our knowledge that includes multi-site and investigator effect in the test design when looking at the effect of different fitting procedures. Adding a by investigator and by treatment interaction term seems to be mandatory if this trial wants to be able to generalize the results for a broader environment. There is no reasonable motivation to add the by site effect as the participants will be randomly assigned to one of the four investigator who should be able to work on both test sites.

3.1 Sample size proposal

Sample size cannot be computed on reported effect sizes from previous experiment, however, the following summary shall be used as an indication to determine the sample size for participants per investigator:

- Naylor et al. (2015) about the narrative effect during the fitting with 24 experienced users and 16 first time users. 83% of the experienced HA users had a preference for a given fitting method and 87.5 % for the first time users. Test design was repeated measures and separate analysis on groups based on experience.
- Dawes et al. (2011) about the placebo effect in hearing aid trials with 20 experienced hearing aid users.
 75% of the listeners had a preference for the labelled "new" hearing aid (effect size = 0.50),
- Dawes et al. (2013) about the placebo effect in hearing aid trials with 16 experienced hearing aid users. 75% of the listeners had a preference for the labelled "new" hearing aid (effect size = 0.66),
- Humes et al. (2017) about the performances with over the counter hearing aids compared to audiology best practice with 154 participants. Between groups test design with 3 arms (placebo, reference device, and over the counter alternative).

Placebo effect was found with sample sizes about 20 participants in single site study design. Adding an investigator effect in the design might bring new insights in this domain but need to have a minimum participant per investigator to reduce imbalance between them. A minimum of 24 participants will be included in the test with 4investigators and at least 6 participants per investigator.

This number is in line with Naylor et al. (2015) proposal who wanted "to compare the effect sizes generated by the experimental contrast in this study with those generated in typical studies of alternative HA systems, so we chose a sample size (n = 24) commensurate with such studies. Approximately 75% of studies comparing alternative HA systems utilize $n \le 25$ (Naylor 2005). Statistical power calculations based on HHIE data from another study of a non-acoustical intervention (Thorén et al. 2014) indicate that n = 18 would be sufficient to detect a 10-point change in HHIE score in either direction with an alpha of 0.05 and a Power of 0.8."

3.2 Power analysis

The expected power as a function of the effect size can be computed with G*Power (version 3.1.9.2).

Preference: χ^2 distribution can be used to investigate if the preference distribution is due to chance or to the manipulated effect. We can compute the effect size from the reported literature with Cohen's w (Cohen, 1988):

$$W = \sqrt{\frac{(p_{0i} - p_{1i})^2}{p_{0i}}}$$

where p_{0i} is the value of the *i*th cell under H0 and p_{1i} is the value of the *i*th cell under H1. However, there are two possible analysis options that can be differentiated by the counting method.

1. with 2 outcomes i.e. there is an audible difference or not,

Naylor (2015) experiment 1: w = 0.67Naylor (2015) experiment 2: w = 0.75Naylor (2015) experiments 1 and 2: w = 0.7Dawes (2011) experiment 1: w = 0.5Dawes (2013) experiment 2: w = 0.5Dawes experiments 1 and 2: w = 0.5All the experiments together: w = 0.6

With an effect size of 0.6, 1 degree of freedom, 24 participants and α of 0.05, we can achieve a power of 0.84. This analysis method is used by Dawes in his papers because only one device was preferred over the other if the listeners had a preference. The influence of effect size variation on the achieved power is show in figure 1.

This analysis allows to answer the question is there is a difference between both method used in the test. But it does not give an indication about the preferred method.

2. with 3 outcomes i.e. preference for A, preference for B, or no preference,

Naylor (2015) experiment 1: w = 0.54Naylor (2015) experiment 2: w = 0.47Naylor (2015) experiments 1 and 2: w = 0.5Dawes (2011) experiment 1: w = 0.94Dawes (2013) experiment 2: w = 0.94Dawes experiments 1 and 2: w = 0.94all the experiments together: w = 0.65

With an effect size of 0.65, 2 degrees of freedom, 24 participants and α of 0.05, we can achieve a power of 0.82. The influence of effect size variation on the achieved power is show in figure 2.

Adding a degree of freedom in the analysis leads to a small loss of power, even if it is always higher than 80%. However, it might give more information about which method will be preferred.

[figure not shown]

Figure 1: Expected power as a function of the effect size with analysis on 2 levels (audible difference or not)

[figure not shown]

Figure 2: Expected power as a function of the effect size with analysis on 3 levels (preference for A, preference for B or no preference)

4. Analysis

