### 11.2 Determination of Sample Size

A literature search about this tested topic does not provide enough strong references to build a confirmatory analysis. It seems that results might be strongly influenced by the inclusion criteria (first time vs experienced hearing aid users) or test design (cross-over, multi-investigator, or between group designs). There is no article to our knowledge that includes a multi-investigator effect in the test design when looking at the effect of different fitting procedures. Adding a -by investigator- treatment interaction term seems to be mandatory if this trial wants to be determine the effect that different investigators have on the fitting procedure.

The sample size cannot be computed on reported effect sizes from previous experiment; however, the following summary shall be used as an indication to determine the sample size for participants per investigator:

•Naylor et al. (2015) about the narrative effect during the fitting with 24 experienced users and 16 first time users,

•Humes et al. (2017) about the performance with over-the-counter hearing aids compared to audiology best practice with 154 participants,

•Dawes et al. (2013) about the placebo effect in hearing aid trials with 16 experienced hearing aid users,

•Dawes et al. (2011) about the placebo effect in hearing aid trials with 20 experienced hearing aid users.

A placebo effect was found with sample sizes of about 20 participants in a single site study design. Adding an investigator effect in the design might bring new insights in this domain but requires a minimum number of participants per investigator to reduce imbalance between them.

With an effect size of 0.65 from the literature review, 2 degrees of freedom, 24 participants, and an alpha of 0.05, we can achieve a power of 0.82. Therefore, a minimum of 24 participants will be included in the trial overall. There will be 4 investigators with 6 to 8 participants per investigator.

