2.1 Primary outcomes

The perceived benefit will be measured with:

- a. the IOI-HA questionnaire and its official translation into German (Cox et al., 2002)
- b. a custom questionnaire based on reference article from Naylor et al. (2015).

These two questionnaires were used in the reference article from Naylor et al. (2015) to measure the effect of narrative embodied in the hearing aid fitting process. Even current research question addresses another aspect of the fitting process, these tools have shown a potential to detect changes in the investigated processes.

IOI-HA questionnaire

Perceived benefit of amplification assessed with 7 questions on a 5 points scale (maximum score 35). Indication from reference study found an effect of fitting process between the preferred and less preferred possibility:

- significant 3.2 scale points and an effect size of 0.68 with experience hearing aid users (n = 24),
- non-significant 0.5 scale points with first time hearing aid users (n = 16).

Custom questionnaire

From the reference study, the questionnaire will directly ask about the preference (much better/slightly better/no difference), the certainty of preference (10 points VAS), and the reason (multiple choice: sound quality, speech intelligibility, listening effort, comfort, loudness, other).

- Fitting procedures: no significant difference between both fitting procedures for first time and experienced hearing aid users,
- Placebo effect: 20 out of 24 indicated a difference with a mean certainty of 7.9/10 for the experienced users group. 14 out of 16 indicated a difference with a mean certainty of 7.0/10 for the first time users group

Order effect

From the reference study, test order might play a different role for first time or experienced users:

- No order effect was found with the experienced hearing aid users,
- A highly significant test order effect in favor for the second tested hearing aid was found for the first time users.

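### The planned preference test ignores the strength and certainty that are collected, and its three-cell form tests equal thirds rather than IMD against RMD, so 0.82 is not power to show a preference

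*SAP*

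**What the plan says.** SAP 2.1 places a custom questionnaire under the primary outcomes and says that "the questionnaire will directly ask about the preference (much better/slightly better/no difference), the certainty of preference (10 points VAS"), plus the reason for the preference. With direction included, the strength item has five ordered levels, from RMD much better through no difference to IMD much better.

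For analysis, SAP 4.1 names "chi2 distribution on the preference test" and Protocol 11.4 names "chi-squared distribution on the preference test". SAP 3.2 describes two ways of counting without choosing between them: "with 2 outcomes i.e. there is an audible difference or not", or "with 3 outcomes i.e. preference for A, preference for B, or no preference". For the first, with w = 0.6 and 1 degree of freedom, the SAP states "we can achieve a power of 0.84". For the second, with w = 0.65 and 2 degrees of freedom, it states "we can achieve a power of 0.82". Protocol 11.2 carries only the second forward: "With an effect size of 0.65 from the literature review, 2 degrees of freedom, 24 participants, and an alpha of 0.05".

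No named test uses strength or certainty. The one other possible place is a principal component analysis of unspecified combinations of variables (SAP 4.1).

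**The concern.** Two things are lost between questionnaire and test. First, much better and slightly better are counted alike, the position of no difference between the two preferences is ignored, and certainty is not used. Second, a chi-square on three unordered cells asks whether A, B and no preference are equally common. The trial's question is whether IMD or RMD is preferred. The two questions come apart whenever few participants report no difference, which is what the reference study found.

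At stake is how the preference result is read, and how n = 24 is justified. A significant three-cell chi-square could be reported as a preference for one fitting method when it reflects only that most people expressed some preference. And 0.82 could be read as power to detect a preferred method, which it is not.

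**Working it through.** **1. The plan's own figures.** Power = P(noncentral chi-square with df and noncentrality n·w² exceeds the 5% critical value), n = 24.
- Two cells: n·w² = 24 × 0.36 = 8.64; critical value 3.84; power 0.836 (stated 0.84).
- Three cells: n·w² = 24 × 0.4225 = 10.14; critical value 5.99; power 0.821 (stated 0.82).

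Both reproduce. The stated three-cell w values can also be rebuilt. A/B/none counts of 14/6/4 and 8/6/2 return 0.54 and 0.47, and 75/0/25% returns 0.94. These A/B counts are inferred, since the documents do not print them. Pooled with the two placebo studies they give 49/12/15 of 76, and w = 0.66 (stated 0.65).

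**2. What the three-cell null does when neither method is preferred.** SAP 2.1 reports that 20 of 24 and 14 of 16 participants indicated a difference. So 4 + 2 = 6 of 40, or 15%, did not. Set the truth to 42.5% IMD, 42.5% RMD and 15% none. Then w = √{3 × [2 × (0.425 − 0.333)² + (0.15 − 0.333)²]} = 0.39, although no method is favoured. Exact enumeration of all outcomes at n = 24 gives a rejection probability of 0.403: 0.185 with more choices for IMD, 0.185 with more for RMD, and the rest tied. With 12.5% none, as in the first-time users, it is 0.529. One example is 11 IMD, 11 RMD and 2 none: chi-square = (3² + 3² + 6²)/8 = 6.75 on 2 df, p = 0.034, with no net preference at all.

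Under its own null of equal thirds the test holds its level (0.050).

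**3. Does using the grading gain power?** The share of much better is not in the documents, so it is assumed and varied. With the pooled split of 64.5% A, 15.8% B and 19.7% none, and n = 24, the three-cell chi-square has 0.83 and a sign test of A against B has 0.82 (asymptotic) or 0.75 (exact). A Wilcoxon signed-rank test on −2 to +2 gives:

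| Much better among A / among B (assumed) | Signed-rank |
|---|---|
| 60% / 20% | 0.91 |
| 50% / 25% | 0.85 |
| 50% / 50% | 0.72 |
| 30% / 60% | 0.57 |

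**4. A latent-shift model.** Assume a normal preference with SD 1, about 15% no difference (cut at 0.19) and 23% to 50% much better at zero shift (cuts at 1.2, 0.9 and 0.67), with 20,000 runs per setting:

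| Shift (SD) | Three-cell chi-square | Sign test, asymptotic (exact) | Signed-rank |
|---|---|---|---|
| 0 | 0.39–0.40 | 0.05 (0.03) | 0.045–0.048 |
| 0.5 | 0.79–0.80 | 0.54–0.55 (0.43) | 0.60–0.61 |
| 0.6 | 0.88 | 0.69 (0.58) | 0.75–0.76 |

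Under this model grading adds about 5 to 8 points over an asymptotic direction-only test. The chi-square rejects more often than either, but it also rejects about 0.40 at zero shift, so its column does not measure evidence of direction.

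**The case against.** The strongest reply has three parts.

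*The planned test is not the weaker one.* A reader might infer that discarding the grading simply costs power. The documents do not support that. Against the test actually planned, signed-rank rejects less often under the latent shift (0.75–0.76 against 0.88 at 0.6 SD). Against a direction-only test, which is not planned, grading gains only if the favoured method also draws the stronger preferences. It loses if strength is equal or reversed between the two groups. No strength distribution is given, so the sign of the difference is an assumption. This part stands in full.

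*The analysis is exploratory.* The Protocol synopsis says so, and Protocol 11.2 says the literature cannot support a confirmatory analysis. The IOI-HA has its own mixed model. The status of preference is also mixed: SAP 2.1 puts the custom questionnaire under primary outcomes, and Protocol 9.2.1 and 11.4.2 mention preference within the primary assessment and analysis, but the study schedule lists it under other variables. This limits the weight of the point. It does not remove it, because the preference chi-square supplies the Protocol's only power figure.

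*The SAP is cautious itself.* It says the two-cell count does not show which method is preferred, and claims only that three cells might tell more. That is fair, but the three-cell test still does not test direction.

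A reader might also infer that 0.82 is miscalculated or that the chi-square has a 40% type I error. Neither is so. The figure reproduces and the test holds 5% under equal thirds; the 40% is rejection under a different, more relevant hypothesis of no net preference.

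**Conclusion.** The point holds as one about what is tested, not as a general loss of power. Ordered strength and certainty are collected and no named test uses them. The three-cell chi-square answers whether the three responses are equally common, and rejects about 40% of the time at n = 24 when 15% report no difference and neither method is favoured. So 0.82 is power against equal thirds only.

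The 40% rests on the 15% no-difference share from the reference study; it is 53% at 12.5%. The comparisons in steps 3 and 4 rest on assumed strength splits and a latent normal model, and step 3 also on the inferred A/B counts. They do not establish a gain from grading. This is a change worth making in an exploratory analysis, since it aligns the test with the question at almost no cost.

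**What to change.** In SAP 3.2 and 4.1, with matching sentences in Protocol 11.2 and 11.4:

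1. Score preference from −2 (RMD much better) through 0 (no difference) to +2 (IMD much better).
2. Name one directional ordinal analysis as the preference test. An ordinal model with test order as a term is preferable, because SAP 2.1 reports a highly significant order effect, favouring the device tried second, in first-time users, who are the population here. A Wilcoxon signed-rank test of the score is the simple version, but has no order term.
3. Use signed certainty (direction times rating) as a supporting analysis.
4. Keep the two- and three-cell counts as a descriptive table.
5. State that 0.82 applies only to the equal-thirds chi-square, and claim no power gain for the graded analysis.

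The cost is wording: the items are already in the questionnaire, and no visits or participants are added. There are two downsides. The signed-rank score assumes ordered steps that are symmetric about no difference. And rejection rates will often be lower than the chi-square's: in step 4, 0.75–0.76 against 0.88 at 0.6 SD. No power has been worked out here for the ordinal model with an order term.
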